### 5.7.2 Objective 2 Primary Effectiveness Outcome

We plan to conduct analyses of subgroups based on: age ( $< 26$  vs older) at randomization; sex; race and ethnicity (Hispanic, Non-Hispanic White, Non-Hispanic Black, Non-Hispanic Asian, Other), using similar subgroups as Objective 1. If one of the subgroups is small (fewer than 5% of patients in the sample), we will consider excluding that category or combining with the “Other” category. To examine whether the treatment effect may differ across groups, we plan to apply the same analytic approach as for the primary analysis of the Objective 2 outcome, in which we will additionally include an interaction term between the categorical subgroup variable of interest and the treatment effect term. As above, such comparisons are expected to be underpowered and will be interpreted cautiously. To aid in the interpretation of potential subgroup-specific effects, we plan to additionally conduct analyses of these subgroups for the patient-level treatment outcome of number of days of OUD medication treatment.

## 6.0 POWER CONSIDERATIONS

### 6.1 Power Simulations for Primary Objective 1 Outcome

The power calculations focus on the six HCS determined to be eligible during Phase 1 of CTN-0074, with each HCS contributing two clinics. One clinic from each HCS will be randomized to implement the PROUD intervention, while the other will continue with usual primary care (UPC). Simulations were conducted to calculate the power associated with various values of the treatment effect, which is parameterized as the mean of the primary outcome measure in the intervention clinics divided by the mean in the UPC clinics. Of ultimate interest in the calculations presented here is whether, with the health systems selected in Phase 1, there will be sufficient power (>80%) to detect at least a 5-fold increase in the number of patient days of OUD treatment (per 10,000 participants) associated with implementation of the PROUD intervention as compared to UPC. To accomplish this, we considered various values of the treatment effect and calculated the corresponding statistical power via simulation.

#### 6.1.1 Data-generation and Analysis Model

In our power simulation, there were 6 HCSs and 2 clinics within each HCS (one clinic assigned to the intervention and one to UPC), making 12 clinics in all.

The outcome variable for each clinic is *Treated Days per Patient Seen*, which with actual data, we would calculate by dividing the total number of treated days at the clinic during 2 years of follow-up by the total number of unique patients seen by the clinic during that same time period. To evaluate power under an analysis approach that adjusts for the baseline value of the outcome, we used Phase 1 data to calculate an approximation of the magnitude of the association between the number of OUD-treated days per patient seen pre- and post-randomization. Using the analytic model specified in Equation (1) would require four years of data for this estimation, however only three years of data are available from Phase 1 (FYs 2014, 2015 and 2016). Thus, data were simulated in a recursive fashion using an autoregressive lag-1 approach.

Step 1: Estimate via regression the relationship between the number of OUD-treated days per patient seen in the last two years of Phase 1 data (2015-2016) and the same measure for the first two years of the Phase 1 data (2014-2015). Letting  $j$  index HCS and  $i$  index clinics within an HCS, this corresponds to regression of the outcome for 2015-2016 on 2014-2015 (see Section 6.1.2). That is, model

$$y_{ij\langle 2015-2016 \rangle} \sim \mu + \rho y_{ij\langle 2014-2015 \rangle}. \quad (2)$$

For this model, a random effect capturing the correlation of clinics from the same health care system was *not* included (see Section 6.1.2). The parameter  $\rho$  captures the association between the number of treated days per patient seen across consecutive years, and the parameter  $\mu$  captures the mean number of treated days per patient seen if no individuals were treated for OUD in the previous year. Let  $\hat{\mu}$  and  $\hat{\rho}$  denote the estimates from the above model.

Step 2: Using this estimated regression model ( $\hat{\mu}, \hat{\rho}$ ), simulate the outcome measure for the next two-year period (2016-2017) for the UPC clinics (i.e.,  $i=1$ ) from

$$\hat{y}_{1j\langle 2016-2017 \rangle} = \varphi + \omega \tilde{y}_{1j\langle 2015-2016 \rangle} + \varepsilon_{1j}$$

where  $\varepsilon_{1j}$  are normally distributed with mean zero and variance  $\sigma_{\varepsilon}^2$ . The parameters  $\varphi$  and  $\omega$  are analogous to  $\mu$  and  $\rho$  from Equation (2). Note that the  $\tilde{y}_{1j\langle 2015-2016 \rangle}$  are generated from a normal distribution with

$$E(\tilde{y}_{1j\langle 2015-2016 \rangle}) = \varphi / (1 - \omega)$$

$$Var(\tilde{y}_{1j\langle 2015-2016 \rangle}) = \sigma_{\epsilon}^2 / (1 - \omega^2)$$

See Appendix B for the justification of these initial values.

**Step 3:** Repeat the simulation for the UPC clinics in the next overlapping two-year period (i.e., 2017-2018) from

$$\hat{y}_{1j\langle 2017-2018 \rangle} = \varphi + \omega \tilde{y}_{1j\langle 2016-2017 \rangle} + \varepsilon_{1j}.$$

**Step 4:** Then repeat the simulation for the UPC clinics a final time for the post-randomization period corresponding roughly to 2018-2019 from

$$\hat{y}_{1j\langle 2018-2019 \rangle} = \varphi + \omega \tilde{y}_{1j\langle 2017-2018 \rangle} + \varepsilon_{1j}.$$

Then simulate the 2018-2019 outcome data for the MA Model clinics (i.e.,  $i=2$ ) from

$$\tilde{y}_{2j\langle 2018-2019 \rangle} = \tau + \tilde{y}_{1j\langle 2018-2019 \rangle} + \pi \vartheta_j$$

where  $j$  are normally distributed with mean zero and variance  $\sigma_{\vartheta}^2$ . Note that  $\vartheta_j$  induces a correlation between the two clinics from HCS  $j$ .

### 6.1.2 Parameters Used to Generate the Simulated Data

Table 3 provides the number of OUD-treated days during a two-year period per patient seen in the clinic. These values were used to estimate the parameters for Steps 1 and 2 in the algorithm summarized in Section 6.1.1.

**Table 3: Number of Days Treated for OUDs (with buprenorphine or injectable naltrexone) per Patient Seen at 2 Phase 1 Clinics in Each of 6 Health Care Systems (HCS)**

HCS	Fiscal Years 2014-2015		Fiscal Years 2015-2016	
	Clinic 1	Clinic 2	Clinic 1	Clinic 2
1	0.031	0.008	0.085	0.019
2	0.339	0.215	0.354	0.173
3	0.001	0.022	0.001	0.076
4	0.015	0.089	0.021	0.431
5	0.007	0.002	0.004	0.002
6	1.385	0.715	1.361	0.703

From Table 3 we fit a random effects model with a fixed intercept for the number of OUD-treated days per patient seen in FYs 2015-2016 as a function of FYs 2014-2015 where the random effect captures the correlation between clinics from the same HCS. The estimated intercept was 0.05, the coefficient for FYs 2014-2015 was 0.94 and the variance of the random effect was not significantly different from zero (in fact, the actual estimated variance was zero). Thus, the predictive model used to generate the simulated data did not include a random effect for HCS (see Section 6.1.1).

The parameters used for this set of simulations are summarized in Table 4 below.

**Table 4: Parameters Explored in the Power Simulation**

Parameter	Value
$\sigma_{\epsilon}$	0.10
$\sigma_{\beta}$	0
$\omega$	0.94
$\varphi$	0.05

### 6.1.3 Results of Simulations

Table 5 presents power results (detectable effect size) for the 0.05-level one-tailed test, based on 10,000 iterations per table cell for two models: one without adjustment for baseline, and one with baseline included as a covariate. The column “Inclusion of Baseline as a Covariate” adjusts for the pre-randomization/baseline value of the primary outcome measure.

**Table 5: Power Results for a 0.05-level One-Tailed Test, Based on 10,000 Iterations Per Cell**

k-fold Increase in Primary Outcome (Treatment Effect)	Model	
	No Adjustment for Baseline	Inclusion of Baseline as a Covariate
1.00	5%	5%
1.06	9%	13%
1.12	15%	29%
1.18	21%	49%
1.24	30%	68%
1.30	39%	84%
1.36	50%	93%
1.42	60%	98%

Based on Table 5, there is at least 80% power to detect a 30% increase in the number of OUD-treated days per patient seen. Thus, with two clinics in each of six HCSs, the study is sufficiently powered to detect the targeted 5-fold increase in the primary outcome measure. As anticipated, there is a substantial gain in power when the baseline value is included as a covariate in the primary outcome model.

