## 5.0 ANALYSES OF OUTCOME MEASURES

### 5.1 Primary Analytic Method for Primary Implementation Outcome Measure

Since randomization and the intervention occur at the clinic-level, the unit of analysis will be clinic and not patient for the primary outcome. The mixed effects model evaluating the effect of the PROUD intervention is:

$$y_{ij} = \alpha + \beta * trt_{ij} + \gamma * z_{ij} + \theta_j + \epsilon_{ij} \quad (1)$$

where

- 1)  $y_{ij}$  is the observed value of the primary outcome measure for clinic  $i$  at health care system (HCS)  $j$
- 2)  $trt_{ij}$  is the treatment indicator (PROUD intervention) for clinic  $i$  at HCS  $j$
- 3)  $z_{ij}$  is the observed value of the primary outcome measure for the two years prior to randomization (hereafter baseline) for clinic  $i$  at HCS  $j$
- 4)  $\theta_j$  is the random effect for HCS  $j$  and is distributed  $N(0, \sigma_{\theta}^2)$
- 5)  $\epsilon_{ij}$  is the error term for clinic  $i$  at HCS  $j$  and is distributed  $N(0, \sigma_{\epsilon}^2)$

Our primary hypothesis is that there will be a significant increase in the number of patient days of medication treatment for OUDs during the follow-up period in clinics randomized to the PROUD intervention as compared to clinics randomized to UPC. To evaluate this hypothesis, analyses test whether  $\beta$  (PROUD intervention effect) significantly exceeds zero using a one-sided hypothesis test at the 0.05 level. This is appropriate because our primary aim is to test superiority of implementation of the MA model relative to Usual PC in order to inform health systems' decisions as to whether to implement this model of OUD care.

Example SAS code for the analysis is as follows:

```
proc mixed data = primout;
  class arm;
  model scaletotdays = arm basevalue / solution;
  random intercept / subject = site;
  estimate "Treatment Effect" arm 1 -1;
run;
```

where "arm" is the treatment assignment ( $trt_{ij}$ ), "scaletotdays" is the value of the primary outcome measure ( $y_{ij}$ ), "basevalue" is the value of the primary outcome measure for the two years prior to randomization ( $z_{ij}$ ) and "site" indexes the different HCSs ( $j$ ).

This model allows for clinics to be correlated within a HCS, in addition to allowing for an association of the scaled days of OUD treatment prior to randomization with the post-randomization outcome.

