### 6.1.4 Potential Exclusion of One Health Care System

At the time power calculations were originally conducted, it was thought possible that one of the HCSs might not be able to participate due to issues with ceding to the single Institutional Review Board (IRB), though this did not end up occurring (instead, this site randomized 6 months late; see Section 2.5). To address this possibility, the power calculations were repeated but using information from only the five other HCSs and the data simulated arise from only five HCSs and ten clinics.

As with the original power calculations, we fit a random effects model to the remaining health systems' data in Table 3 with a fixed intercept for the number of OUD-treated days per patient seen in FYs 2015-2016 as a function FYs 2014-2015 where the random effect captures the correlation between clinics arising from the same HCS. The parameter estimates from this model did not change substantially. The estimated intercept was 0.05, the coefficient for FYs 2014-2015 was 0.94 and the variance of the random effect was not significantly different from zero. Thus, the predictive model used to generate the simulated data did not include a random effect for HCS. Table 6 summarizes the results of these additional simulations.

**Table 6: Power Results for a 0.05-level One-Tailed Test, Based on 10,000 Iterations Per Cell with Five Health Care Systems**

k-fold Increase in Primary Outcome (Treatment Effect)	Model	
	No Adjustment for Baseline	Inclusion of Baseline as a Covariate
1.00	5%	5%
1.03	8%	12%
1.06	12%	25%
1.09	16%	40%
1.12	22%	59%
1.18	35%	87%
1.24	49%	98%

With only five HCSs, the study will still be powered sufficiently to detect at least 80% power to detect an 18% increase in the number of OUD-treated days per patient seen. Specifically, the power to detect a 1.18-fold increase in the per patient primary outcome measure is 87%. Thus, with two clinics in each of five HCSs, the study is sufficiently powered to detect the targeted 5-fold increase in the primary outcome measure.

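### SAP Table 6 (five systems) contradicts corrected Table 5 and appears to be pre-correction; Table 5's 30% is relative to an unreported mean about three times the Phase 1 level

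*SAP*

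**What the plan says.** SAP section 6.1 defines the treatment effect as a ratio, "parameterized as the mean of the primary outcome measure in the intervention clinics divided by the mean in the UPC clinics". The question it sets is whether "there will be sufficient power (>80%) to detect at least a 5-fold increase in the number of patient days of OUD treatment". In section 6.1.1 "there were 6 HCSs and 2 clinics within each HCS", and each simulated series starts from a normal distribution with mean φ/(1−ω), justified in Appendix B. Section 6.1.2 gives the fit to the Phase 1 data: "The estimated intercept was 0.05, the coefficient for FYs 2014-2015 was 0.94". Table 4 uses those two values with a residual SD of 0.10 and an HCS SD of zero. The test in section 5.1 is one-sided at 0.05.

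From Table 5, section 6.1.3 concludes that "there is at least 80% power to detect a 30% increase in the number of OUD-treated days per patient seen". With the baseline covariate, that table shows 49% power at 1.18-fold and 84% at 1.30-fold.

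Section 6.1.4 repeats the exercise for five HCSs. It reports estimates of 0.05 and 0.94 again and says, from Table 6, that "the power to detect a 1.18-fold increase in the per patient primary outcome measure is 87" per cent. Both sections close by concluding that a 5-fold increase can be detected.

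Protocol Modification 10 says the previous primary-outcome power results came from a program with a typo, and prints a regenerated Table 13 whose values are those of SAP Table 5. The SAP's overview of changes says the Objective 1 power calculations were updated to match. Section 6.1.4 does not say whether Table 6 was included.

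**The concern.** There are two separate problems.

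First, dropping from twelve clinics to ten, with the same intercept and slope, takes power at 1.18-fold from 49% to 87%. That cannot happen, so one of the two tables is not what it is said to be.

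Second, a percentage increase means little without its base. The simulation's base follows from φ and ω, but the SAP never prints it or compares it with the Phase 1 values in Table 3. A reader will naturally take a 30% increase to mean 30% above what these clinics were delivering.

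At stake are the quantified power statements for the primary objective: what size of relative increase the trial could detect, and whether five systems would have sufficed for an 18% increase.

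**Working it through.** **Inputs.** φ = 0.05, ω = 0.94, residual SD 0.10 and HCS SD 0 (SAP Table 4); 6 HCSs × 2 clinics; one-sided 0.05; Phase 1 values from Table 3.

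**Step 1: reproduce Table 5.** The starting mean is 0.05/(1 − 0.94) = 0.833 and the starting SD is 0.10/√(1 − 0.94²) = 0.293. The intervention adds (k − 1) × 0.833. Baseline (2016–17) and outcome (2018–19) are two recursion steps apart, and clinics are taken as independent within an HCS. The analysis is a REML mixed model with an HCS intercept and a t test on 4 degrees of freedom (containment), with 10,000 runs per cell.

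| k | Table 5, adjusted | Reproduced |
|---|---|---|
| 1.00 | 5% | 5.3% |
| 1.06 | 13% | 13.9% |
| 1.12 | 29% | 28.8% |
| 1.18 | 49% | 48.3% |
| 1.24 | 68% | 69.5% |
| 1.30 | 84% | 84.2% |
| 1.36 | 93% | 93.0% |
| 1.42 | 98% | 97.6% |

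The unadjusted column also agrees within 2 points. So Table 5 is a correct calculation, and k multiplies 0.833.

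**Step 2: the same program with five HCSs (3 degrees of freedom).**

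| k | Table 6, adjusted | Computed |
|---|---|---|
| 1.03 | 12% | 9% |
| 1.06 | 25% | 12% |
| 1.09 | 40% | 17% |
| 1.12 | 59% | 24% |
| 1.18 | 87% | 40% |
| 1.24 | 98% | 57% |

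- At 1.18-fold, ordinary least squares gives 43% and the mixed model with residual degrees of freedom gives 51%. The most conservative choice gives about 30%.
- Putting baseline only one step before the outcome gives 57 to 71% for five HCSs. That already exceeds Table 5's 49% for six, so it is not the model behind Table 5, and it still falls short of 87%.
- 80% power needs k of about 1.34 (mixed model) or 1.31 (least squares).
- Reaching 87% at 1.18-fold would need a residual SD near 0.05. Refitting Table 3 without HCS 1, 2, 3 or 5 keeps the estimates near 0.05 and 0.94 and gives an SD of 0.11. Only dropping HCS 4 gives a small SD (0.029), but the estimates then become 0.014 and 0.97, which is not what section 6.1.4 reports.

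**Step 3: where Table 6 may come from.** Its grid of k values is that of the superseded Table 13 in Protocol section 11.4.1.3, and its power values sit just below that table's:

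| k | Superseded Table 13 (six HCSs) | Table 6 (five HCSs) |
|---|---|---|
| 1.03 | 14% | 12% |
| 1.06 | 28% | 25% |
| 1.09 | 46% | 40% |
| 1.12 | 65% | 59% |
| 1.18 | 92% | 87% |
| 1.24 | 99% | 98% |

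Inflating the effect by an empirical factor of about 1.94 reproduces the superseded column within 2 points. The same factor reproduces Table 6 within 1 point by least squares, or within about 5.5 points by the mixed model. The superseded table is used here only as evidence; Modification 10 already replaces it.

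**Step 4: the base of the 30%.**
- Phase 1 mean, FY 2015–16: 3.230/12 = 0.269. Only one of the twelve clinics (1.361) exceeds 0.833. Ratio: 0.833/0.269 = 3.1.
- The SAP's recursion run forward: 0.05 + 0.94 × 0.269 = 0.303, then 0.335, then 0.365 for 2018–19.
- Shift at k = 1.30: 0.30 × 0.833 = 0.25 days per patient. Per 10,000 patients this is 2,500 patient-days, or 2,500/365 = 6.8 patient-years.
- 0.25/0.365 = 0.68 and 0.25/0.269 = 0.93, so the same shift is a 1.68- to 1.93-fold increase.
- A true 30% rise on 0.269 is 0.081 days and has about 22% power. On 0.365 it is 0.110 days and has about one-third power. Both figures keep the SD at 0.10.

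**Step 5: the 5-fold target.** On 0.269 the shift is 4 × 0.269 = 1.08 days, over four times the 0.25 above. Power is about 100% with six or five HCSs.

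**The case against.** Much of the defence stands.

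- **Table 5 is not an error.** It follows from printed inputs, and the starting distribution is disclosed in section 6.1.1 and Appendix B. A reader might infer that the 84% is miscalculated; it is not. What is missing is the reference level.
- **The design conclusion does not depend on either point.** The SAP's stated interest is a 5-fold increase, and the number of systems was set by eligibility (Protocol section 11.4). A reader might infer that the trial is underpowered for its target; the figures do not support that. A reader might also suspect that 5-fold power would fail if the effect varied between systems. The simulation assumes an equal effect and the documents give no size for such variation, so no figure can be put on it.
- **The five-system case never arose**, as section 6.1.4 itself says. Table 6 still stands in the SAP beside a corrected table that contradicts it.
- **That Table 6 was never rerun is an inference.** It is a strong one, from the grid and the values, but the SAP does not say so. The contradiction with Table 5 needs no inference.
- **The re-anchored figures lean on the SD of 0.10**, which one clinic drives (HCS 4, clinic 2: 0.089 to 0.431). Without it the refitted SD is 0.027. The 84%-power shift would then scale to about 0.25 × 0.027/0.10 = 0.068 days, or 25% of 0.269. The 1.7- to 1.9-fold range is therefore conditional on the SAP's own SD.
- **The Step 4 formula.** Read literally with a zero HCS SD, it makes each intervention clinic a copy of its usual-care partner plus a constant, and a reader might infer that it cannot yield Table 5. Symbols in that passage appear to have been lost in text extraction, so it does not support a charge against the plan.
- **Misreading a null result** is a possibility, not something the SAP proposes. The shell for the sensitivity analyses calls for mean differences with confidence intervals, and interpretation should rest on those.

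**Conclusion.** The point holds in two limited parts, and its severity is moderate.

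1. Table 6 is inconsistent with Table 5 and appears to be pre-correction. On the Table 4 inputs, five-HCS power at 1.18-fold is about 40% (roughly 30 to 50% across degrees-of-freedom choices), not 87%. The claim of 80% power for an 18% increase is unsupported; about 1.31- to 1.34-fold on the simulated mean is needed.
2. Table 5 stands as arithmetic, but its 30% is relative to 0.833 treated days per patient. Against Phase 1 or projected levels, the same 0.25-day shift is about a 1.7- to 1.9-fold increase.

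This rests on independent clinics within an HCS and a two-step gap between baseline and outcome, both supported by the match to Table 5. Part 2 also assumes that the SD of 0.10 carries over to the lower mean. Adequate power for a 5-fold increase is unchanged under the SAP's equal-effect model.

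**What to change.** - **Section 6.1.3:** state that the design has 84% power for an absolute increase of 0.25 treated days per patient (2,500 patient-days per 10,000). Give the simulated usual-care mean of 0.833. Add that the shift is about a 1.7- to 1.9-fold increase on projected (0.365) or Phase 1 (0.269) levels, assuming a residual SD of 0.10.
- **Section 6.1.4:** rerun Table 6 with the corrected code, or delete the table and the sentences giving 18% and 87%. Since the contingency has passed, deletion is enough.
- **Both sections:** keep the 5-fold conclusion and say that it assumes an equal effect across systems.

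The cost is SAP wording and at most one rerun of existing code. The design, the outcome and the primary analysis do not change; the stated detectable relative increase becomes less favourable.

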### 6.1.4 Potential Exclusion of One Health Care System

At the time power calculations were originally conducted, it was thought possible that one of the HCSs might not be able to participate due to issues with ceding to the single Institutional Review Board (IRB), though this did not end up occurring (instead, this site randomized 6 months late; see Section 2.5). To address this possibility, the power calculations were repeated but using information from only the five other HCSs and the data simulated arise from only five HCSs and ten clinics.

As with the original power calculations, we fit a random effects model to the remaining health systems' data in Table 3 with a fixed intercept for the number of OUD-treated days per patient seen in FYs 2015-2016 as a function FYs 2014-2015 where the random effect captures the correlation between clinics arising from the same HCS. The parameter estimates from this model did not change substantially. The estimated intercept was 0.05, the coefficient for FYs 2014-2015 was 0.94 and the variance of the random effect was not significantly different from zero. Thus, the predictive model used to generate the simulated data did not include a random effect for HCS. Table 6 summarizes the results of these additional simulations.

**Table 6: Power Results for a 0.05-level One-Tailed Test, Based on 10,000 Iterations Per Cell with Five Health Care Systems**

k-fold Increase in Primary Outcome (Treatment Effect)	Model	
	No Adjustment for Baseline	Inclusion of Baseline as a Covariate
1.00	5%	5%
1.03	8%	12%
1.06	12%	25%
1.09	16%	40%
1.12	22%	59%
1.18	35%	87%
1.24	49%	98%

With only five HCSs, the study will still be powered sufficiently to detect at least 80% power to detect an 18% increase in the number of OUD-treated days per patient seen. Specifically, the power to detect a 1.18-fold increase in the per patient primary outcome measure is 87%. Thus, with two clinics in each of five HCSs, the study is sufficiently powered to detect the targeted 5-fold increase in the primary outcome measure.

